Initial evaluation of each mother's carotenoid status will be obtained prior to starting any study supplements. Subsequent evaluations while participants are taking the study supplements will be performed in conjunction with routine prenatal visits to their Obstetrician, at approximately 22-26 weeks gestational age and again at 37-39 weeks gestational age. All mothers will undergo a final assessment within two weeks of giving birth.

Infants' evaluations will be performed in the first two weeks of life, either during the original hospital stay or at a follow up outpatient clinic visit.

Visit:	Screening/ Baseline	Maternal Supplementation		
	T1	T2	T3	Birth
Timeframe:	Before 14 Wks GA	22-26 Wks GA	37-39 Wks GA	0 to 2 Wks
Informed Consent	X			
Randomization	X			
Maternal visual acuity and contrast sensitivity	X	X	X	X
Maternal nutritional surveys	X	X	X	X
Dilated eye examination	X			
Maternal serum carotenoids	X	X	X	X
Maternal macular pigment imaging	X	X	X	X
Maternal skin carotenoids	X	X	X	X
Dispense prenatal supplement and do pill counts	X	X	X	X
Infant cord blood carotenoids				X
Infant macular pigment imaging				X
Infant foveal imaging (sdOCT)				X
Infant skin carotenoids				X

Unscheduled Visits

Mothers may be seen for Unscheduled Visits if deemed necessary for repeat measurements or follow-up of Adverse Events. If a mother delivers her baby prematurely, she and her infant will remain in the study and will be asked to complete the final study visit.

Description of Study Assessments:

Visual Function - Manifest refraction, and measurement of best-corrected visual acuity and contrast sensitivity of the mothers will be obtained by certified ophthalmic technicians using standardized protocols. The study staff performing visual acuity will be masked to the treatment assignment. Best-corrected visual acuity testing will be assessed on ETDRS back-lit charts starting at a distance of 4 m, and should precede any examination requiring administration of eye drops to dilate the eye or any examination requiring contact with the eye. Contrast sensitivity will be measured by the Pelli-Robson threshold contrast sensitivity chart at 1 m.

Maternal Eye Exam - The complete ophthalmic exam will consist of the following:

- External examination of the eye and adnexa.
- Routine screening for eyelids/pupil responsiveness (including ptosis, abnormal pupil shape, unequal pupils, abnormal reaction to light and afferent pupillary defect).

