Maternal Macular Pigment Levels - Mothers' macular pigment will be measured using the dual wavelength autofluorescence method which measures attenuation of lipofuscin autofluorescence by blue absorbing macular pigment. The subject looks at a fixation target with her dilated study eye for about 30 seconds as her macula is scanned sequentially with alternating 486 nm (blue) and 518 nm (green) lasers, and autofluorescence images are collected. Macular pigment images are prepared by digitally subtracting the green image from the blue image using appropriate correction factors to compensate for the absorption spectrum of the macular carotenoid pigment and then analyzed using macular pigment analysis software after setting the zero point at 9 degrees of eccentricity. This instrument and software has proven to be highly reliable and reproducible, especially when measuring macular pigment volume under the curve at 9 degrees.

Serum Carotenoid Levels - Blood samples obtained from mothers and from infant cord blood will be analyzed for serum carotenoid content using well-established laboratory protocols that can provide baseline separations of all common dietary carotenoids. Whenever possible blood samples will be obtained by piggy backing onto a routine clinical blood collection.

Dietary Questionnaires - At each study visit mothers will be asked to complete the LZQ quantitative food frequency questionnaire that captures ~90% of the lutein/zeaxanthin foods consumed in the US, based on National Health and Nutrition Examination Survey data.

Safety Evaluations - Any clinically significant abnormalities persisting at the end of the study/ early withdrawal will be followed by the investigator until resolution or until a clinically stable endpoint is reached. The study includes procedures to monitor safety, including complete Ophthalmic exams and monitoring of adverse events.

Optional Specimen Collection and Banking Sub-Study

Participants will be asked to allow a sample of placenta tissue to be collected and stored for future research related to maternal to infant carotenoid transport on a tissue level.

Participants will be asked to provide a saliva sample to be stored and used for future research related to the genetics of carotenoid metabolism enzymes.

Participants will be asked to allow a portion of their blood collected at study visits to be stored for future research related to the genetics of carotenoid metabolism.

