Subgroup analyses will be performed to assess the influences of maternal dietary carotenoid intake, compliance with study supplement use, co-existing medical conditions, BMI, infant gender, and other factors on our study results, with proper attention to the effects of multiple tests on the ability to draw conclusions.

The complete statistical analysis plan will be finalized prior to database lock, and will provide statistical methods as well as descriptions of how missing, unused and spurious data will be addressed. Summarization of study data will be prepared of subject demographics, baseline characteristics, and investigational product exposure.

Safety Analyses

Serious and unexpected adverse events will be collected from the time of the first study supplement administration until a subject completes the study or discontinues prematurely. Treatment emergent adverse events (TEAEs) are defined as those AEs that develop or worsen after the first dose of study supplement and up to 30 days beyond the last dose of study medication. The current version of MedDRA will be used to classify all AEs.

Treatment- emergent adverse events will be summarized by System Organ Class and Preferred Term, in accordance with the MedDRA coding dictionary. The number of subjects reporting each AE preferred term will be tabulated for all TEAEs and separately for those considered as related to study treatment by the Principal Investigator. The number of subjects reporting SAEs will also be tabulated. Adverse event summaries will be presented for each treatment group separately.

Adverse events will be summarized by MedDRA coding terms, and separate tabulations also will be produced for related adverse events (those considered by the Investigator as definitively drug related), serious adverse events and discontinuations due to adverse events. Findings from ophthalmologic examinations will be tabulated for changes over time on study. Separate summaries will be prepared for systemic (non-ocular) and ocular AEs, with events in the study eye and non-study eye summarized separately.

Title: Lutein & Zeaxanthin in Pregnancy (L-ZIP) - Carotenoid Supplementation During Pregnancy: Ocular and Systemic Effects

Consent Process

1. The following investigators and internal staff will obtain consent (as indicated on the Study Location and Sponsors Page):

[name]	University of Utah
[name]	University of Utah
[name]	University of Utah
[name]	University of Utah

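### The adverse-event collection rule is narrower and shorter than the TEAE tables it must fill, and fundus, slit-lamp and IOP findings have no scheduled later value for a change table

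*Combined protocol and SAP*

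**What the plan says.** Three parts of 4. Study Information bear on this.

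**Item 9, Safety Analyses.** The collection rule is "Serious and unexpected adverse events will be collected from the time of the first study supplement administration until a subject completes the study", and the full stopping condition is "until a subject completes the study or discontinues prematurely". The next sentence defines TEAEs as events that begin or worsen after the first dose and "up to 30 days beyond the last dose of study medication". On tables, "The number of subjects reporting each AE preferred term will be tabulated for all TEAEs", with a separate count of those judged related. Further, "The number of subjects reporting SAEs will also be tabulated", and discontinuations due to adverse events get their own table. The section also plans a table showing how eye-examination findings change during the study.

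**Item 6, Study Visit Schedule.** "All mothers will undergo a final assessment within two weeks of giving birth", shown in the schedule as 0 to 2 weeks. No later contact is scheduled. The row "Dispense prenatal supplement and do pill counts" is marked at T1, T2, T3 and Birth. The dilated eye examination is marked at T1 only. Acuity and contrast sensitivity, and maternal macular pigment imaging, are marked at all four maternal visits. Unscheduled visits are allowed where judged necessary.

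**Item 6, Description of Study Assessments.** The maternal eye examination consists of external, pupil, slit-lamp, dilated fundus and IOP assessments. The IOP bullet asks for one consistent method across a woman's measurements, which presumes more than one. Safety Evaluations cites full eye examinations and adverse-event monitoring in general terms and adds: "Any clinically significant abnormalities persisting at the end of the study/ early withdrawal will be followed by the investigator".

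**The concern.** A table of all TEAEs will be read as covering every adverse event, of any seriousness, from first dose to 30 days after the last. The only stated collection rule does not supply that. It names a restricted type of event and stops at study exit, while the TEAE window is tied to the last dose and can close later.

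The incidence counts could therefore be too low in either arm. Nothing in the documents shows by how much, or that the shortfall would differ between arms. The full SAP, still to be finalized before database lock, can redefine a table but cannot recover events that were never recorded.

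The eye table has a similar problem on a smaller scale. A change needs a later value, and for fundus, slit-lamp and IOP findings none is scheduled.

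**Working it through.** The plan states no figure to reproduce here. The check sets its rules side by side and counts days and visits.

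**1. Period**

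Inputs:
- *v*, day of the final visit after birth: 0 to 14 (Study Visit Schedule).
- *d*, day of last dose relative to birth: not stated, so varied.
- TEAE window: closes on day *d* + 30 (Safety Analyses).
- Collection: ends at completion, taken as day *v*.

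Uncovered days = max(0, 30 − (*v* − *d*)).

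| Last dose | Calculation | Uncovered days |
|---|---|---|
| Day of birth, visit on day 0 | 30 − 0 | 30 |
| Day of birth, visit on day 7 | 30 − 7 | 23 |
| Day of birth, visit on day 14 | 30 − 14 | 16 |
| Day of final visit | 30 − 0 | 30 |
| 7 days before birth | 30 − 21 to 30 − 7 | 9 to 23 |
| 14 days before birth | 30 − 28 to 30 − 14 | 2 to 16 |
| 30 or more days before birth | *v* − *d* is at least 30 | 0 |
| After the final visit | 30 + (*d* − *v*) | all 30, plus the later on-dose days |
| Supplement and study stopped the same day | 30 − 0 | 30 |

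Late dosing cannot be ruled out from the text. The dispensing and pill-count row is marked at Birth, and the administration instruction in the Investigational Drug Data Form mentions lactation as well as pregnancy.

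Nothing else closes the gap. The Safety Evaluations sentence follows abnormalities already present at exit, not new events. Unscheduled visits happen on demand.

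**2. Scope**

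| Event type | Collected if the phrase means serious *or* unexpected | Collected if it means both | In the planned tables |
|---|---|---|---|
| Serious, unexpected | yes | yes | yes |
| Serious, expected | yes | not stated | yes (all TEAEs and SAEs) |
| Non-serious, unexpected | yes | not stated | yes (all TEAEs) |
| Non-serious, expected | not stated | not stated | yes (all TEAEs) |

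On either reading at least one tabulated category has no stated collection.

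**3. Eye findings**

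The dilated eye examination has one mark among four maternal visits, at T1, so 0 of 3 post-baseline visits. Slit-lamp and IOP have no row of their own. Placing them under the dilated-examination row is an inference, but without it they have no scheduled visit at all. Acuity, contrast sensitivity and macular pigment imaging are scheduled at 3 of 3 post-baseline visits and are not affected.

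**The case against.** **Scope.** The Investigational Drug Data Form says no physical risks are expected from the softgels, and it names skin discoloration only at very large doses. If expectedness is judged against product information, nearly every event is unexpected, and the *or* reading then comes close to collecting everything. The stricter reading also sits poorly with a plan that codes all adverse events and tabulates related events, SAEs and discontinuations. This narrows the gap, but only on one reading and only under a standard of expectedness that the text never states. Ordinary events of pregnancy are not classified at all.

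**Period.** A TEAE definition classifies events and does not itself promise to collect them. It still does useful work for a woman who stops the supplement but stays in the study. That is fair, but the definition also labels the table, and a reader will take the label as the coverage. The day counts depend on the assumed last-dose date and are calendar days, not missed events; that limit stands.

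**Eye findings.** The change-over-time sentence does not name fundus, slit-lamp or IOP, and repeated acuity and imaging could fill a table. But the sentence refers to ophthalmologic examinations, and the plan's own description of the eye examination consists of the components scheduled only at T1. An incomplete schedule row is possible, and that is a reason to reconcile the sections.

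**Other documents.** Item 9 asks for a summary, and the background section points to a longer protocol that is not supplied. A wider collection rule might be there. If so, this text still has to be brought into line with it.

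The safety summaries are descriptive, in 60 mothers, and no hypothesis test is affected. That argues for a modest severity; the mismatch remains.

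**Conclusion.** The concern holds: the safety section is wrong as written on the text supplied.

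- **Period:** 16 to 30 of the 30 post-dose days are uncovered for a completer whose last dose falls between birth and the final visit, assuming that completion means the final visit. Across other last-dose dates the gap runs from 0 to all 30 days, and beyond if dosing continues after that visit. It is 30 of 30 for a same-day stop of supplement and study.
- **Scope:** non-serious expected events are outside the stated collection on any reading. Serious expected events, and non-serious unexpected ones, are outside it as well on the stricter reading.
- **Eye findings:** fundus, slit-lamp and IOP have 0 of 3 scheduled post-baseline values. This is the narrower point.

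The documents do not show that any event was actually missed. The effect on counts is unknown, and no difference between arms is claimed. This should be corrected before the tables are produced; it does not touch the efficacy analysis.

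**What to change.** **Adverse events: choose one.**

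*Option A, if follow-up is still open.* State that all adverse events, serious or not and expected or not, are collected from the first study supplement through 30 days after the last dose, including after early discontinuation where the woman can be reached. Cost: one brief remote contact per woman and slightly more data entry. Some who leave early will not be reachable.

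*Option B, if follow-up is finished.* Restrict the TEAE definition and every table title to the event types and period actually collected, for example serious or unexpected events from first supplement to completion or discontinuation. Cost: wording only, but the tables then say less about the time after the last dose and about any event type not collected.

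Under either option, record each woman's last-dose date and define what serious and unexpected means, including the reference against which expectedness is judged.

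**Eye findings.** Reconcile the Study Visit Schedule with the Maternal Eye Exam, Safety Evaluations and Safety Analyses text. Alternatively, limit the change table to acuity, contrast sensitivity and macular pigment imaging at T1, T2, T3 and Birth, and list the other examination findings at T1 and at any unscheduled visit. Limiting the table costs wording only.

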Participation in these procedures is optional and participants may decline any or all of them and still participate in the main study. Participant identifiers will be stored separately from the banked samples and participants will be able to withdraw their samples if they so desire.

Banked samples may be shared with other researchers, who must have IRB approval for their use and material/data transfer agreements with the University of Utah as applicable.

7. Are all procedures for research purposes only (non-standard or non-standard of care procedures)?

Yes No

If no, list the procedures that are performed for research purposes only (non-standard or non-standard of care procedures):

All Protocol-specified procedures are for research purposes only, with the exception of dispensing prenatal supplements. Expectant mothers will be taking prenatal supplements whether or not they agree to participate in this study.

8. Is there a safety monitoring plan for this study?

Yes No

9. Provide a summary of the statistical methods, data analysis, or data interpretation planned for this study. Factors for determining the proposed sample size (e.g., power) should be stated.

Statistical Analysis

The study outcome data will be analyzed by a consultant from the University of Utah Study Design and Biostatistics Center of the Center for Clinical and Translational Science.

Image analysis of retinal camera macular pigment measures will be conducted in [name] laboratory. Foveal anatomy parameters such as width, depth, and layer structure will be assessed by Drs. [name] and [name] using methods based on previously published protocols.

Sample Size Calculation and Power Considerations

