The prenatal multivitamin tablets will be stored in the Moran Eye Center Clinical Studies Storage room and dispensed by the study coordinator.

The softgels and multivitamins will only be accessible to authorized and trained staff members.

11. Location of Drug Supply:

Other

Moran Eye Center Pharmacy and Moran Eye Center Clinical Studies Storage Room

12. Storage Requirements:

Room Temperature

If Other, Please Explain:

Store with cap secured at room temperature. Avoid extreme temperatures.

13. Emergency Drug Information (include name and phone number):

[name], PhD
[contact]

PI: [name]

Submitted: 11/21/2018

Title: Lutein & Zeaxanthin in Pregnancy (L-ZIP) -
Carotenoid Supplementation During Pregnancy:
Ocular and Systemic Effects

Investigational Use of a Device

1. What is the initial risk determination of the device study according to the investigator and/or sponsor?

The study is a non-significant risk (NSR) device study.

a. Provide IDE (or HDE) Number(s) for significant risk devices:

IDE #	Device Name	IDE Holder
-------	-------------	------------

There are no items to display

b. Attach verification of the IDE number for significant risk devices to the Documents and attachments page. Please check the method by which you choose to verify the IDE number:

There are no items to display

2. Describe the plan to control, store, and dispense the investigational device. This plan should ensure that the device is only used by qualified investigator(s) for the participants enrolled in this research project.

There are two investigational devices being used in this study. The first is the Heidelberg MOPD module software program used to analyze carotenoid levels in the macula, the second is the skin scanner. [name] personally oversees the use of the Heidelberg system. He does not allow use of the software program for routine medical care. [name] is a patent holder for the scanner and personally control access to the scanner and train study staff in its use. He does not allow use of the skin scanner for routine medical care, nor would it be relevant to standard care.

IRB_00116610

Created: 10/1/2018 12:13
PM

IRB_00116610

- - Non Significant Risk Device

PI: [name]

Submitted: 11/21/2018

Title: Lutein & Zeaxanthin in Pregnancy (L-ZIP) -
Carotenoid Supplementation During Pregnancy: Ocular
and Systemic Effects

Non-Significant Risk Device

Review the following definition of a non-significant risk (NSR) device:

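### Adverse-event collection opens at the first supplement dose, after the research-only baseline procedures, so events with onset before that dose, or in women never dosed, fall outside the stated window

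*Combined protocol and SAP*

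**What the plan says.** All references are to the combined protocol and SAP.

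- **Start of collection** (4. Study Information, item 9, Safety Analyses): "Serious and unexpected adverse events will be collected from the time of the first study supplement administration". Collection runs until the woman completes the study or leaves it early.
- **Treatment-emergent events** (same section): "those AEs that develop or worsen after the first dose of study supplement and up to 30 days beyond the last dose".
- **Order at baseline** (item 6, Study Visit Schedule): "Initial evaluation of each mother's carotenoid status will be obtained prior to starting any study supplements". The schedule marks the rows "Maternal macular pigment imaging" and "Maternal skin carotenoids", and the serum row, at T1, T2, T3 and Birth. It marks the dilated eye examination at T1 only. The T1 column is headed as screening and baseline and stands ahead of the columns for supplementation.
- **Content of the procedures** (item 6, Description of Study Assessments): macular pigment imaging uses a dilated study eye. The complete exam includes slit lamp, dilated fundus exam and Tono-pen tonometry.
- **Status of the procedures** (item 7): "All Protocol-specified procedures are for research purposes only, with the exception of dispensing prenatal supplements".
- **Devices** (Investigational Use of a Device, item 2): "There are two investigational devices being used in this study". They are the macular pigment analysis software and the skin scanner.

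**The concern.** Starting at the first dose suits tables meant to describe a supplement's effects. It does not suit the collection of harms from study procedures when those procedures begin earlier. Here every participant's first exposure to the research measurements comes before the window opens, and the participants are pregnant women, whom the application lists as a vulnerable group. Someone applying the rule literally has no instruction to record an event that starts during or soon after the T1 procedures but before the first softgel. A woman randomised at T1 who never starts the supplement is never in the window at all.

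There is a smaller, related gap. The treatment-emergent definition counts events that worsen after the first dose. Judging that needs a record of what was present before, and nothing in the text requires pre-dose symptoms to be recorded.

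At stake is the completeness of the safety record for procedures and devices. No efficacy result depends on it, nor does the comparison of treatment-emergent events between arms.

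**Working it through.** The plan gives no figure to reproduce. The check sets the collection window against the visit schedule and then counts sessions.

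**Step 1: what precedes the first dose.** For serum, skin and macular pigment this is stated outright, since the first carotenoid evaluation comes before any supplement. For the complete dilated exam it is an inference from its place in the baseline column.

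**Step 2: which events the stated window covers.**

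| Event | Inside the window? |
|---|---|
| Onset after the first T1 procedure and before the first dose, no later worsening | No |
| Any event in a woman randomised but never dosed | No |
| Caused by a T1 procedure, but first appearing after the first dose | Yes |
| Present before the first dose, worsening after it | Yes, but recording the pre-dose symptom is not required |
| Caused by imaging, skin scan or blood draw at T2, T3 or Birth | Yes |

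Each yes refers to timing only. The sentence also limits collection to serious and unexpected events, and that limit applies at every visit.

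**Step 3: is an earlier start stated elsewhere?** Three other places bear on it:

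- the unscheduled-visit text (item 6), which allows adverse-event follow-up;
- the Safety Evaluations text (item 6), which mentions adverse-event monitoring;
- 5. Data Monitoring Plan, item 4, which provides for a check that appropriate information has been reported.

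None gives a start time, so none displaces the explicit one.

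**Step 4: count of sessions.** Inputs are 60 mothers (3. Participants, item 4) and 4 maternal visits (visit schedule), assuming full attendance.

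- Sessions per device: 60 × 4 = 240.
- Before the first dose: 60 × 1 = 60, and 60 / 240 = 25%.
- Inside the window: 60 × 3 = 180, or 75%.
- Scheduled complete dilated exams: 60 × 1 = 60, all at T1, so 60 / 60 = 100% by the schedule.

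The documents give no event rate and no time from the T1 procedures to the first dose. The number of events missed therefore cannot be calculated.

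**The case against.** The strongest reply is that the practical loss is very small, and most of that reply stands.

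- **Low risk.** 6. Risks and Benefits expects no risk from the skin measurement's light exposure, puts imaging light within safety limits, and treats the dilating drops as standard of care. The Non-Significant Risk Device section explains that the investigational imaging item is analysis software on a cleared instrument that acquires images in its usual way, so the software adds no physical exposure. Blood is taken with routine draws where possible.
- **Short interval.** Supplements are dispensed at T1, so the first dose may follow soon after.
- **The exam count is less certain than it looks.** The tonometry text speaks of using one method across a woman's measurements during the study, and item 9 plans to tabulate ophthalmic findings over time. Both suggest repeat exams that the schedule does not mark.

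The reply does not supply an earlier start, and low expected risk does not justify leaving out what does occur.

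A reader might also infer stronger things that the documents do not support:

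- **That faints or drop reactions at T1 are lost because of the start date.** Most would be neither serious nor unexpected, so the same sentence would omit them at T2, T3 or Birth as well.
- **That a condition already present at T1 cannot be told apart from a new one.** Eye exam, acuity, contrast sensitivity and medical eligibility are all assessed at baseline, and item 9 plans summaries of baseline characteristics. The gap is baseline symptoms, whose recording is not spelled out.
- **That pre-dose harms never reach the IRB or a monitoring board.** The sentence stands in a statistical summary, and the monitoring plan has its own reporting check. The answer on a safety monitoring plan (item 8) cannot be read in this copy. The Background also points to a protocol reference list that is not included. A separate reporting rule or an earlier start stated elsewhere cannot be ruled out.

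**Conclusion.** The point holds as a narrow gap that is cheap to close. On the text available, events with onset between the first study procedure and the first dose, and all events in women randomised but never dosed, are outside the only stated collection window. The procedures concerned are ones the application itself calls research-only.

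The 25% is a share of scheduled device sessions at full attendance. It must not be read as a quarter of harms missed, because the uncovered interval may be short and three of the four sessions are covered. Few missed events are expected.

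The conclusion rests on two assumptions: that the collection sentence is applied as written, and that no document outside this file sets an earlier start. Including the complete dilated exam also rests on its position in the schedule; the blood draw, skin scan and imaging need no such inference.

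**What to change.** Change the collection sentence and add three short provisions:

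1. Collect adverse events from signed consent or the first study procedure, for every enrolled woman whether or not she takes a dose.
2. Keep the first dose as the start of the treatment-emergent tables.
3. List pre-dose events separately, each with its relation to a study procedure or device.
4. Record symptoms present at baseline, so that later worsening can be judged.

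Separately, reconcile the limit to serious and unexpected events with the same section's plan to tabulate all treatment-emergent events. Unless that is done, moving the start will not capture non-serious procedure events at any visit.

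The cost is a little protocol wording and a few more entries at a visit already held. No visit, procedure or staff is added, and clinical care does not change.

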Title: Lutein & Zeaxanthin in Pregnancy (L-ZIP) - Carotenoid Supplementation During Pregnancy: Ocular and Systemic Effects

Investigational Drug Data Form

- 1. Name of Investigational Drug:** Lutein-2mg Zeaxanthin Softgels
- 2. Synonyms:**
Softgel containing 10 mg lutein, 2 mg zeaxanthin, and safflower oil.
- 3. Manufacturer or Other Source:** Kemin Health, Des Moines, IA
- 4. Other Study Drugs:**
Placebo softgel (Kemin Health) containing safflower oil (control group will receive).
Prenatal vitamins (all participants will receive)
- 5. Type of Study (Blinding Information):**
Double-masked
- 6. Strength(s) and Dosage Form(s):**
The active study supplement, Kemin Health Lutein-2mg Zeaxanthin softgel, is a commercially available, over the counter product containing 10 mg of lutein and 2 mg zeaxanthin per softgel.
- 7. Indications for Use and Pharmacology:**
Nutritional supplement
- 8. Possible Side-Effects/Adverse Reactions:**
Kemin Health softgels with Lutein/zeaxanthin are within the standard of care expectant mothers would receive if they were not in the study. There are no expected physical risks associated with the supplements.
- 9. Drug Administration Information**
 - a. Usual Therapeutic Dose:**
1 softgel per day (10 mg lutein, 2 mg zeaxanthin)
 - b. Dosage Range:**
1 softgel per day
 - c. Therapeutic Blood Levels:**
unknown (not routinely tested in standard care)
 - d. Route of Administration:**
Oral
 - e. Rate of Administration for IV Infusion or Push:**
N/A
 - f. Reconstitution Directions (include stability info):**
N/A
 - g. Precautions and Special Instructions for Administration:**
During pregnancy and lactation take one softgel daily with food.
 - h. Toxicology and Antidote:**
There are no known toxic effects of taking too much zeaxanthin. Very large doses of carotenoids such as lutein and zeaxanthin can cause carotenodermia - a yellow-orange skin discoloration. It can look like jaundice, but the abnormal skin color can be removed with an alcohol swab. In case of

overdose do not induce vomiting. Contact Poison Control, physician or pharmacist for advice.

10. Describe the plan to control, store, and dispense the investigational drug. This plan should ensure that the drug is only used by qualified investigator(s) for the participants enrolled in this research project.

The Kemin softgels will be stored in and dispensed by the Moran Eye Center Pharmacy.

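### Safety Analyses uses two inconsistent criteria for a related adverse event, one limited to definite cases, so suspected events can be left out of a related-event table

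*Combined protocol and SAP*

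**What the plan says.** The relevant text is two consecutive paragraphs of Safety Analyses (Section 4, Study Information, item 9).

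- The first paragraph plans a count of subjects for every TEAE by preferred term, whatever the cause. A second count in the same sentence is restricted by causality: "separately for those considered as related to study treatment by the Principal Investigator". The paragraph also tabulates SAEs and ends "Adverse event summaries will be presented for each treatment group separately".
- The second paragraph says that "separate tabulations also will be produced for related adverse events", and its parenthesis explains which events are meant: "related adverse events (those considered by the Investigator as definitively drug related". Serious events and discontinuations due to adverse events get their own tables in the same sentence.

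The Investigational Drug Data Form gives the setting in which causality is judged. The trial is "Double-masked" (item 5). The control group receives an oil softgel and all participants receive prenatal vitamins (item 4). On side effects, item 8 says "There are no expected physical risks associated with the supplements".

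**The concern.** The same section uses the label *related* with two criteria, and a statistician programming the tables could not tell from the text which events belong in which. The second criterion is also an unusual one for a tolerability table. An investigator who does not know the assignment, and who has the multivitamin and pregnancy itself as competing explanations, may well suspect the softgel without being able to call the link definite. Events of that kind are the ones a related-event table is normally meant to show. At stake is whether the causality-based part of the safety report is consistent and whether it captures suspected effects of a supplement given in pregnancy.

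**Working it through.** The plan states no figure on this point, so there is none to reproduce. The check is a comparison of the two criteria.

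| Element | First paragraph | Second paragraph |
|---|---|---|
| Events covered | TEAEs | adverse events |
| Assessor | Principal Investigator | Investigator |
| Related to | study treatment | drug |
| Certainty required | none stated | definitive |
| Status | main tabulation | additional ("separate tabulations also will be produced for related adverse events") |

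The document contains no causality scale (such as possible, probable, definite) and no rule linking the two columns. That leaves two readings.

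1. **The criteria differ.** An event that the investigator suspects but cannot confirm enters the first table and not the second. The report then holds two tables of related events that can disagree.
2. **The parenthesis defines the term for both.** The tables agree on certainty, but a suspected event that is not definite appears in neither.

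These are alternatives, so the two consequences do not add up. Under both readings, at least one related-event table leaves out suspected events that are not definite.

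**How much is lost.** Let *p* be the share of investigator-suspected events that are graded definite. The share missing from the strict table is 1 − *p*. The document does not give *p*, so the values below are assumptions:

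| Assumed *p* | Share missing, 1 − *p* |
|---|---|
| 2% | 98% |
| 5% | 95% |
| 10% | 90% |
| 20% | 80% |
| 30% | 70% |
| 50% | 50% |

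A loss of at least 90% requires *p* to be 10% or less. Masking, the shared multivitamin and the statement that no physical risks are expected all make a definite grade less likely. They do not fix *p* within this range.

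**What is unaffected.** Four outputs do not depend on the criterion: the table of all TEAEs by preferred term, the SAE table, the discontinuation table, and the ophthalmologic findings over time.

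**The case against.** The strongest reply is that little is lost. In a randomized, masked trial the comparison of all TEAEs between arms needs no attribution by the investigator, and that table is planned by treatment group. This stands, and it is the main reason the point is of moderate weight. It does not repair the related-event tables, which the plan has chosen to produce. The all-TEAE table also depends on what is collected, and the collection sentence in the same subsection names only events that are serious and unexpected.

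A second reply is that the first paragraph sets no threshold, so the plan has one definition and not two. That is a fair reading. It removes the disagreement between tables but extends the strict criterion to both.

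A third is that item 9 is a summary, that the complete SAP is to be finalized before database lock, and that a full protocol is cited but not reproduced here. A causality scale may exist there. If so, these two paragraphs still have to be aligned with it. Grades also have to be recorded when events are assessed, because they cannot be rebuilt reliably at lock.

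Three stronger inferences should be resisted.

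- A reader might infer that nearly all suspected effects would vanish, or that the table would be near zero whatever the supplement does. The document gives no event rate and no share graded definite, so neither claim can be supported. Setting 4 of the 30 women planned per arm (13%) with suspected events against 0 of 30 definite only restates the assumption that *p* is zero.
- A reader might infer that harm would be hidden from the report as a whole. The tables that do not use causality contradict this.
- The drug form's statement "Very large doses of carotenoids such as lutein and zeaxanthin can cause carotenodermia - a yellow-orange skin discoloration" might be taken as an effect that the strict table would miss. It concerns very large doses and says nothing about how events on the study softgel would be graded.

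**Conclusion.** The point holds. Safety Analyses uses inconsistent criteria for a related adverse event, and the stricter one leaves suspected but uncertain events out of the second table, or out of both if the parenthesis governs both. For any given set of events the direction is certain, because adding a requirement of definiteness can only remove cases. The extent is unknown: an assumed definite share of 50% down to 2% gives a loss of 50% up to 98%, and nothing in the document narrows that range. The conclusion rests on the wording of the two paragraphs and on the absence of a reconciling rule in the public text. It should be corrected, but it affects descriptive causality tables only. It does not touch the efficacy analysis or the between-arm display of all TEAEs.

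**What to change.** In Safety Analyses:

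- use one definition of *related* and one named assessor role for both tabulations;
- delete the word definitively;
- count any TEAE that the masked investigator judges at least possibly related to the study supplement;
- state that the judgement is recorded before unmasking;
- if a definite-only table is still wanted, keep it as an extra table under that label.

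The cost is a short wording change and a causality category on the AE form. The downside is that the reported number of related events may be higher. Any events already assessed without a graded category would need the masked investigator's judgement added before assignments are revealed.
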